5.4 Interim Analyses

No interim analyses are planned.

5.5 Multicenter Study

This is a multicenter study. Seven clinical sites within the United States will participate in the study.

5.6 Multiple Comparisons / Multiplicity

For the primary endpoint and key secondary endpoint 1, 95% confidence intervals will be presented.

For the remaining key secondary endpoints, the fixed sequence method of statistical testing will be used. In order to control the overall type I error rate, these key secondary efficacy endpoints will be tested in a hierarchical, gatekeeping manner in the order specified in Section 4.2. If one key secondary efficacy endpoint does not meet statistical significance in favor of NTX100, formal testing of subsequent key secondary efficacy endpoints will not be conducted.

5.7 Examination of Subgroups

No hypothesis testing is planned on subgroups.

6.0 ANALYSIS POPULATIONS

6.1 Intent-to-Treat (ITT) Population

The Intent-to-Treat (ITT) Population will include all eligible subjects who pass screening and are enrolled into the study. The ITT Population Set will be used for the primary analysis of all efficacy endpoints.

6.2 Stable Medication Population

The Stable Medication (SM) Population will include all eligible subjects who pass screening, are enrolled into the study, and do not report any of the following changes to prescription RLS medication between completion of the RESTFUL Study and Week 24 of CT-05:

- 1. New prescription RLS medication.
- 2. Change in dose of prescription RLS medication.
- 3. New prescription sleep medication.
- 4. Change in dose of prescription sleep medication.

The Stable Medication Population will be used for a secondary analysis of key secondary efficacy endpoints #6-11. This is intended to account for the differences in instructions regarding changes to prescription medications for Arms 1 and 2.

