16.10. Concomitant Medications and Treatments

Concomitant medications and treatments are tracked throughout the study based on subject reported data. For Arms 1 and 3 (but not Arm 2), study subjects are instructed to maintain a stable dose and schedule of all concomitant medications and treatments for RLS and of all concomitant medications and treatments that affect RLS symptoms, including antidepressants, sleep medications, or sedative antihistamines.

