3.5 Changes to the Protocol-Specified Analyses

SAP Version 1.0.

No changes were made to the analysis of the primary efficacy endpoint or key secondary efficacy endpoints #1-5 specified in the protocol. The definition, ordering, and statistical treatment of each remains the same. Consistent with the protocol, the intent-to-treat population will be used to analyze the primary and key secondary efficacy endpoints.

The following changes and additions were made to key secondary analyses:

- 1. Key secondary endpoints #6-11 were added, comparing Arm 1 to Arm 2 at Week 24.
- 2. The Stable Medication (SM) Population was added as a mechanism for additional supportive analysis. This is intended to account for the differences in instructions regarding changes to prescription medications affecting RLS and/or sleep for Arms 1 and 2.
- 3. The definition of the Per Protocol Population was simplified.

Additional clarifications, additions, and modifications were made that do not affect the statistical treatment of the primary or key secondary endpoints.

SAP Version 2.0.

1. For the primary efficacy endpoint (CGI-I Responder Rate), the original null hypothesis was that the Responder Rate is equal to 0 and the null hypothesis was that the Responder Rate is greater than 0. Since a single observation of a Responder would disprove this null hypothesis, this hypothesis test is not a meaningful analysis. Therefore, for the primary

- efficacy endpoint, hypothesis testing has been replaced with presentation of 95% confidence intervals.
- 2. The same issue affected the first key secondary efficacy endpoint (PGI-I Responder Rate) and thus the same change was made.
- 3. As a result of changes 1-2, hierarchical hypothesis testing began with the second key efficacy endpoint (IRLS total score).
- 4. Tables were expanded to include 95% confidence intervals for each key secondary endpoint.

Additional clarifications, additions, and modifications were made that do not affect the statistical treatment of the primary or key secondary endpoints.

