9.0 OTHER ANALYSES

For each of the following outcome measures (CGI-I responder rate, PGI-I responder rate, IRLS total score, MOS-II score, MOS-I score, IRLS Question #7 score), data will be summarized for:

- Each of Arm 1 and Arm 2 at Week 24 for subjects assigned to each of NTX100 and Sham control in CT-04 Phase 1.
- Each of Arm 1 and Arm 2 at Week 24 compared to CT-05 study entry.
- Each of Arm 1 and Arm 2 at each of CT-04 study entry, CT-04 week 8, CT-05 week 8, CT-05 week 16, CT-05 week 24, [and CT-05 week 32 for Arm 1 only].

For CGI-I and PGI-I, data will be summarized for the proportion of subjects reporting any improvement, as measured by a response of 3 or lower (Minimally improved, Much improved, or Very much improved) and reported for each of Arm 1 Week 24, Arm 1 Week 32, and Arm 2 Week 24.

For MOS Sleep, data will be summarized and effect sizes will be presented for each Arm each of the following dimensions and items for each of CT-04 study entry and CT-05 week 24:

- MOS "Sleep disturbance" dimension (Items 07, 03, 08, 01)
- MOS "Somnolence" dimension (Items 09, 11, 06)
- MOS "Sleep adequacy" dimension (Items 04, 12)
- MOS "Quantity of sleep / Optimal sleep" dimension (Item 02)
- MOS Item 01 (Trouble falling asleep)

For each of the following components of SF-36, data will be summarized and effect sizes will be presented comparing Arm 1 of CT-05 study entry to Arm 1 CT-05 week 24 and comparing Arm 1 CT-05 week 24 to Arm 2 CT-05 week 24:

- Vitality
- Physical functioning
- Bodily pain
- General health perceptions
- Physical role functioning
- Emotional role functioning
- Social role functioning
- Mental health

Consent and completion rates will be presented for Arm 1.

Changes to RLS management: For subjects in each Arm, changes to RLS management will be presented including the following:

- Doctor visits for the management of RLS.
- New prescription medications added for the treatment of RLS.
- Prescription medications discontinued for the treatment of RLS.
- Increases to dosage of prescription medication for the treatment of RLS.

• Decreases to dosage of prescription medication for the treatment of RLS. For each, total numbers of subjects and percentages of subjects will be summarized by Arm from Week 1 to Week 24.

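### The Stable Medication Population does not name drug discontinuation and leaves out two drug classes covered by the arm-specific medication instruction

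*SAP*

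**What the plan says.** SAP 6.2 keeps an enrolled subject in the SM Population unless one of four changes is reported between the end of RESTFUL and Week 24 of CT-05: "New prescription RLS medication", "Change in dose of prescription RLS medication", "New prescription sleep medication" or "Change in dose of prescription sleep medication". It gives the reason: "This is intended to account for the differences in instructions regarding changes to prescription medications for Arms 1 and 2". SAP 3.5 gives the same reason with a wider scope: "changes to prescription medications affecting RLS and/or sleep for Arms 1 and 2".

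The instruction that differs between arms is in Protocol 16.10. Arms 1 and 3, but not Arm 2, are to hold dose and schedule stable for RLS treatments and for other treatments that affect RLS symptoms, "including antidepressants, sleep medications, or sedative antihistamines".

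SAP 9.0 tabulates changes to RLS management by arm. It has separate entries for added drugs, dosage increases, dosage decreases and "Prescription medications discontinued for the treatment of RLS".

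**The concern.** Arm 1 versus Arm 2 is an open-label, non-randomised comparison in which one arm is asked to freeze its medication and the other may change it. The SM analysis (SAP Table 2.7) is the only one planned that addresses this difference. SAP 5.2 rules out covariate adjustment, and the medication exclusion in the Per Protocol Population applies to Arm 1 only, so it removes no Arm 2 subject for a medication change.

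If the SM set keeps subjects who stopped an RLS or sleep drug, or who changed an antidepressant or sedative antihistamine, its result can still carry part of the confounding it is meant to remove. A reader shown agreement between the ITT and SM results would then be more reassured than the definition justifies.

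**Working it through.** The plan states no sample size, standard deviation or medication-change rate for this comparison, so there is no figure to reproduce. The check is a comparison of texts.

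| Event | Covered by Protocol 16.10 instruction (Arm 1, not Arm 2) | SM exclusion in SAP 6.2 | Own entry in SAP 9.0 |
|---|---|---|---|
| New RLS drug | yes | yes | yes |
| RLS dose raised or lowered | yes | yes | yes, two entries |
| RLS drug stopped | yes | not named | yes |
| New sleep drug, or sleep dose changed | yes | yes | no |
| Sleep drug stopped | yes | not named | no |
| Antidepressant started, stopped or dose changed | yes | not named | no |
| Sedative antihistamine started, stopped or dose changed | yes | not named | no |

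**Discontinuation.** SAP 9.0 separates stopping from lowering a dose. SAP 6.2 separates starting from changing a dose and has no matching item for stopping. On the SAP's own vocabulary, stopping is therefore not a dose change. For sleep drugs this rests on the parallel wording of 6.2, because SAP 9.0 covers RLS treatment only. A switch is caught, since the replacement is a new prescription.

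**Drug classes.** Inclusion criterion 8 also names antidepressants and sedative antihistamines as affecting RLS; Protocol 7.1 re-assesses it for Arm 1 but not Arm 2. Protocol 16.16 allows removal for a significant dose change in these classes in Arms 1 and 3 only. The SM criteria already reach beyond RLS drugs by including sleep drugs, so a restriction to RLS medication does not explain the omission.

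**Illustration of size (all inputs assumed).** Let f be the net share of Arm 2 SM subjects with an uncaptured change, beyond any such share in Arm 1, and d the mean shift in those subjects. The Arm 2 mean moves by f × d.

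- In IRLS points, with f = 5% to 20% and d = 3 to 5 points: 0.05 × 3 = 0.15 up to 0.20 × 5 = 1.0, in either direction.
- In SD units, with d = 0.5 to 1.0: 0.05 × 0.5 = 0.025 up to 0.20 × 1.0 = 0.20.

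With no device effect and n per arm, the one-sided 0.025 test of SAP 8.2 rejects with probability about Φ(f·d/√(2/n) − 1.96) if the changes worsen Arm 2, and Φ(−f·d/√(2/n) − 1.96) if they improve it.

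- n = 20, f·d = 0.025: √(2/20) = 0.316 and 0.025/0.316 = 0.079, giving 3.0% or 2.1%.
- n = 60, f·d = 0.20: √(2/60) = 0.183 and 0.20/0.183 = 1.095, giving 19.4% or 0.1%.

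The nominal rate is 2.5%. The range only shows how the effect scales; it is not an estimate for this trial.

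**The case against.** A change in dose can be read to include a change to zero, and a descriptive list in SAP 9.0 does not define a term used in SAP 6.2. This stands in part. A reader might infer that the SM set definitely retains everyone who stopped a drug; the text supports only that they stay in or are undefined. Two programmers could classify the same subject differently, which is reason enough to settle the wording.

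On drug classes, SAP 3.1 and 3.2 describe the instruction for RLS medication only, and SAP 6.2 speaks of prescription medications. An antidepressant or antihistamine prescribed for sleep might already count as a sleep drug. The limit to prescription drugs stands: for non-prescription antihistamines the gap is against Protocol 16.10, not the SAP's stated aim. But SAP 3.5 and the protocol both set a wider scope than 6.2 delivers.

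Part of the problem will be visible anyway: Table 2.18 and Listings 3 and 5.1 cover RLS-management changes and medications. That shows how many stopped an RLS drug, but it does not correct the SM comparison.

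Two further inferences are tempting. One is that misclassification is concentrated in Arm 2. The instructions make this plausible, but no change rates are given. The other is that the bias favours the device. A drug may be stopped after improvement or after worsening, so no direction follows.

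**Conclusion.** The point holds as a gap between the SM definition and its stated purpose. The omission of the two drug classes follows directly from the text. The discontinuation part rests on reading SAP 6.2 with SAP 9.0 and is, at the least, an ambiguity that affects who is analysed.

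Its reach is limited. The SM Population gives a secondary analysis of endpoints #6-11 only; ITT remains the primary analysis for all efficacy endpoints. Neither the size nor the direction of the effect can be determined from the documents. The definition should be corrected because the SM analysis is the only planned check on this source of confounding.

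**What to change.** Add three exclusions to SAP 6.2:

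- (5) discontinuation of a prescription RLS medication;
- (6) discontinuation of a prescription sleep medication;
- (7) start, discontinuation or dose change of a prescription antidepressant or prescription sedative antihistamine.

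Apply all seven rules identically in both arms, and report the number excluded by rule and arm with Table 2.7. If analysis has already begun, present the revised set as a labelled sensitivity analysis.

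The edit is a wording change, with three costs. The SM set becomes smaller. More subjects are excluded on post-enrolment events that may be related to outcome; the existing four rules already do this, and the new ones extend it.

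Ascertainment is also unequal. The assessment tables schedule concomitant medications at every evaluation, so a reader might infer that all the data are collected prospectively. That fails for late Arm 2 entrants. Cohort 2B may enrol 8, 16 or 24 weeks after RESTFUL (Protocol 16.2), and those enrolling at 24 weeks have medications assessed only once (Protocol 16.12). Changes before enrolment depend on retrospective report, and the SAP should state this as a limitation.

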16.1. Overview

Arms 1 and 3 involve a 24-week extension of in-home investigational device usage for subjects who previously completed the RESTFUL Study, followed by an 8-week period without investigational device usage to assess the progression of RLS following cessation of treatment. Two separate arms are employed to maximize the number of subjects eligible for any extension phase (Arm 1 and Arm 3) while also maximizing the number of subjects who can proceed directly to the extension phase (Arm 1 only). Notably, in the RESTFUL Study, subjects will have already completed either 4-weeks of device usage (Sham \rightarrow Active) or 8-weeks (Active \rightarrow Active) depending on randomization. Since site staff were blinded to RESTFUL Study treatment assignment, no procedures in this protocol will be affected by RESTFUL Study treatment assignment.

Arm 2 serves as a control arm with matched duration to the 24-week period of investigational device usage; this arm is designed to the assess the changes to medication and RLS symptoms that occur under the conventional standard of care, in the absence of investigational device intervention. Although the duration of Arm 2 states 24-weeks, each subjects participation will vary, since the 24-week period also includes the time between when the subject exits the RESTFUL study and when they enroll in Arm 2 of the CT-05 study. For example, subjects who are consented more than 8-wks after RESTFUL Study completion will only complete the remaining follow-ups (e.g. subjects consented 12-wks after the RESTFUL Study will only complete the 16-wk and 24-wk follow-ups).

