3.1 Overview

Subjects who previously completed the RESTFUL Study [Protocol Number: CT-04; ClinicalTrials.gov Identifier: NCT04874155] consent to one of two Arms, the design of which is

illustrated in the flowchart below (Figure 1). Arm 1 is a Direct Roll-Over Extension and Arm 2 is a Control.

- **Arm 1** (Direct Roll-Over Extension) Arm 1 is only an option for subjects who successfully complete RESTFUL Study after enrollment to CT-05 begins at a given clinical site; Arm 1 involves a 24-wk extension period of NTX100 device use followed by an 8-wk period without device use. Subjects in Arm 1 are instructed to maintain constant dose and schedule of RLS medication (if applicable).
- Arm 2 (Control Group) Arm 2 is an option for subjects who successfully complete the RESTFUL Study before enrollment to CT-05 begins at a given clinical site or subjects who decline to participate in Arm 1. Subjects enrolled in Arm 2 will receive no treatment with the NTX100 device during Arm 2. Arm 2 involves assessment during the 24-wks after RESTFUL Study completion. Subjects in Arm 2 are permitted to change RLS medication.

Figure 1: Study Design Flowchart

The schedule of assessments for this study is presented in Table 1.

Table 1: Schedule of Assessments

	Eval 1			Eval 2	Eval 3	Eval 4	Eval 5	Eval 6	Eval 7	Eval 8	Eval 9	
	Day 0	Wks 1-24	Wks 25-32	Wk-2	Wk-4	Wk-8	Wk-12	Wk-16	Wk-20	Wk-24	Wk-32	
	In-person	Remote	Remote	Remote	Remote	In-person or Remote**			Remote	In-person	Remote	
Completed by												
	X											
	X											
Staff + subject	X											
Subject		X										
Subject			х									
Staff				X	X	x	X	x	X	X		
Staff	X			Х	Х	x	X	Х	Х	х	X	
Staff				X	Х	x	X	x	X	Х	X	
Staff + subject				Х	Х	x	Х	Х	Х	х	X	
Staff + subject				X	X	x	X	x	X	X	X	
Investigator + subject						х		х		Х	X	
Staff + subject					Х	x	X	Х	х	х	X	
Staff + subject	X									х		
Staff + subject										х		
Staff + subject											X	
Staff + subject	X **					X **		X **				
	* Data from Eval	11 of the RE	STFUL Study	will be us	ed, since b	oth Evals typic	cally occu	r on the same	day			
	Staff + subject Subject Subject Staff Staff Staff Staff Staff + subject Staff + subject Investigator + subject Staff + subject	In-person	Day 0 Wks 1-24 In-person	Day 0	Day 0 Wks 1-24 Wks 25-32 Wk-2	Day 0	Day 0	Day 0	Day 0	Day 0 Wks 1-24 Wks 25-32 Wk-2 Wk-4 Wk-8 Wk-12 Wk-16 Wk-20 In-person or In-pe	Day 0 Wks 1-24 Wks 25-32 Wk-2 Wk-4 Wks-4 Wks-12 Wk-16 Wk-20 Wk-24	Day 0

		Eval 1	Eval 2	Eval 3	Eval 4	

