3.2 Method of Assigning Subjects to Treatment

All subjects who are enrolled in Arm 1 will be assigned to:

- NTX100 programmed to ACTIVE mode for Weeks 1-24
- No treatment for Weeks 25-32

and will be instructed to maintain constant dosage and schedule of RLS medication (if applicable) for Week 1-32.

All subjects who are enrolled in Arm 2 will be assigned to:

• No treatment for Weeks 1-24 and will be permitted to change RLS medication during the study.

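### The Stable Medication set does not account for the arms' different medication instructions: it selects on a change that those instructions govern, and it keeps subjects lost without a medication record as stable

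*SAP*

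**What the plan says.** SAP 6.2 defines the Stable Medication set as eligible, enrolled subjects who "do not report any of the following changes to prescription RLS medication between completion of the RESTFUL Study and Week 24 of CT-05". The listed changes are a new prescription, or a changed dose, of an RLS or sleep medication. On use, it says: "The Stable Medication Population will be used for a secondary analysis of key secondary efficacy endpoints #6-11". Its stated purpose is: "This is intended to account for the differences in instructions regarding changes to prescription medications for Arms 1 and 2".

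The instructions differ by arm. SAP 3.2 assigns Arm 1 to the active device for Weeks 1-24 "and will be instructed to maintain constant dosage and schedule of RLS medication (if applicable) for Week 1-32". For the control group, SAP 3.1 says: "Subjects in Arm 2 are permitted to change RLS medication". Protocol 16.16 also makes a significant dose change a possible reason for removal in Arms 1 and 3 only.

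The protocol treats medication change as an outcome. Of Arm 2, Protocol 16.1 says "this arm is designed to the assess the changes to medication and RLS symptoms that occur under the conventional standard of care", and Protocol 17.2.4 lists medication change among the Arm 1 versus Arm 2 outcomes.

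The set is supportive. SAP 3.5 states: "The Stable Medication (SM) Population was added as a mechanism for additional supportive analysis". SAP 6.1 makes ITT primary for all efficacy endpoints. Missing efficacy data are filled by LOCF, from CT-04 if there are no CT-05 data (SAP 5.3), and no covariate adjustment is planned (SAP 5.2).

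**The concern.** Whether a subject changes medication after RESTFUL plausibly depends on how symptoms develop, and certainly depends on whether the arm permits it. Dropping those who change does not put the arms on an equal footing. It turns a difference in instructions into a difference in who is retained. If the Arm 2 subjects who change are mainly those doing badly, the Arm 2 subjects who remain look better than the whole arm, while Arm 1 loses few.

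The wording has a second effect. The per-protocol set requires Week 24 data and excludes discontinuations; the Stable Medication set requires neither. A subject lost early with no reported change is classed as stable and enters with an LOCF value. Every RESTFUL completer ended on the active device (Protocol 16.1). An Arm 2 subject with no CT-05 efficacy data can therefore sit in the stable, no-device group with an on-device score.

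Table 2.7 is the only planned efficacy comparison that handles medication change in both arms: the per-protocol set removes medication changers in Arm 1 only, and Table 2.18 is descriptive. A reader told that the set accounts for the instructions may take Table 2.7 as the corrected estimate. It could then hide part of a real device effect or, through lost Arm 1 subjects, overstate one.

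**Working it through.** The documents give no SD, medication-change rate, dropout rate or effect size for this comparison, so there is no figure to reproduce. Every input below is an assumption. Differences are Arm 1 minus Arm 2 in mean IRLS reduction; a negative value favours Arm 2.

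**1. Selection, closed form.** Removing the worst fraction q raises the retained mean by ρ × SD × φ(z)/(1−q), where z is the normal cut-off for q and ρ is the correlation between outcome and changing. Take SD 7 and no device effect.
- Arm 2, q = 0.30: φ = 0.3477; 7 × 0.3477/0.70 = 3.48.
- Arm 1, q = 0.05: φ = 0.1031; 7 × 0.1031/0.95 = 0.76.
- Spurious shift towards Arm 2: 3.48 − 0.76 = 2.72 points at ρ = 1, and 1.36 at ρ = 0.5.

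**2. Selection, simulated over a range.** SD 8, no true difference, 400,000 subjects per arm, with the chance of a change rising with worse symptoms by a logit slope per SD:

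| Removed, Arm 1 / Arm 2 | Slope 0 | Slope 1 | Slope 2 |
|---|---|---|---|
| 5% / 5% | 0.0 | 0.0 | 0.0 |
| 5% / 20% | 0.0 | −1.0 | −1.5 |
| 5% / 30% | 0.0 | −1.6 | −2.4 |
| 5% / 40% | 0.0 | −2.3 | −3.3 |
| 15% / 30% | 0.0 | −1.0 | −1.4 |

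Both conditions are needed: change related to symptoms, and unequal frequency. With a true difference of 5 and 5%/30% removed, the set gives 5.0 at slope 0, 3.3 at slope 1 and about 2.6 at slope 2.

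**3. Responder endpoints.** Suppose 30% of Arm 2 would respond without a medication change, and 10% of responders and 40% of non-responders change. The retained rate is 0.30 × 0.90/(0.30 × 0.90 + 0.70 × 0.60) = 0.27/0.69 = 39%.

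**4. Lost subjects kept as stable.** Assume a mean reduction of 10 on the device and 5 off it, and that LOCF carries forward 10.
- 30% of Arm 2 lost, none of Arm 1: truth 10 − 5 = 5.0; estimate 10 − (0.70 × 5 + 0.30 × 10) = 3.5; bias −1.5.
- 20% of Arm 1 lost, none of Arm 2: truth (0.80 × 10 + 0.20 × 5) − 5 = 4.0; estimate 10 − 5 = 5.0; bias +1.0.
- Equal loss in both arms: zero on these inputs.

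**5. Ascertainment.** In the Protocol 16.12 schedules, Arm 1 has eight concomitant-medication checks by Week 24 (Evals 1-8) and Arm 2 at most four. Arm 2 subjects enrolled at 24 weeks have one. Relying on reported changes is therefore a weaker screen in Arm 2.

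**The case against.** The strongest reply is that the documents establish no bias. They give no rates of, or reasons for, medication change, so a link to symptoms is an inference. That stands: without such a link, or with equal rates, the selection shift is zero.

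The worse-tail model is also narrower than the rule. A change in dose includes decreases, and SAP 9.0 foresees them. A subject who reduces a dose because symptoms eased is dropped too, which works the other way. The 2.7-point figure needs a correlation of 1, a limiting case.

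The consequence is limited. The set is supportive, and under SAP 8.2 the fixed sequence turns on the primary analyses, so Table 2.7 gates no formal test. The selection route alone would not create a false device claim. In a simulation with 45 per arm, no true difference and 5%/30% removed, rejection in favour of Arm 1 fell to about 0.2% (slope 1) or 0.02% (slope 2), against a nominal 2.5%. LOCF affects ITT as well. Table 2.18 and Listings 3 and 5.1 would let a reader see how unequal the changes were.

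A reader might go further and infer that Table 2.7 is biased against Arm 1 by a known amount, or that pairing it with an analysis that errs the other way would bracket the true effect. The documents support neither. The arms are not randomised, Arm 2 includes subjects who declined Arm 1, and nothing is adjusted, so two analyses can miss on the same side.

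None of this rescues the purpose sentence or the rule that treats an absent report as stability. Both follow from the SAP text.

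**Conclusion.** The point holds in a limited form. Membership of the Stable Medication set is decided after RESTFUL completion by behaviour that the arms' instructions govern and that the protocol treats as an outcome. The set therefore cannot account for those instructions. For Cohort 2B the window also covers time before CT-05 enrolment, so the selection is after RESTFUL completion rather than strictly after entry to this study.

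Table 2.7 may be biased if changes are related to symptoms and differ in frequency between arms. The likely direction is against Arm 1. Size and net direction cannot be fixed from the documents: 1.4 to 2.7 IRLS points is correct arithmetic on assumed inputs, dose decreases and lost Arm 1 subjects push the other way, and zero is possible. Separately, and without any such assumption, the wording classes a subject lost without a reported change as stable. This is a correction to a supportive analysis; the ITT analysis and the formal testing sequence are untouched.

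**What to change.** 1. In SAP 6.2, count a subject as stable only if concomitant medication is documented from RESTFUL completion through Week 24. For Arm 2 subjects enrolled late, state that the record must look back to RESTFUL completion.
2. Replace the purpose sentence in SAP 6.2, and the matching one in SAP 3.5, with a statement that the set is selected after RESTFUL completion, is descriptive, does not remove the difference in instructions, and may be biased in either direction.
3. Beside Table 2.7, add a supportive ITT analysis of endpoints 6 and 7 in which a new or increased RLS or sleep prescription in either arm counts as non-response. Label it a sensitivity analysis that may favour Arm 1, because Arm 2 is the arm allowed to change. Do not claim that the two analyses bracket the true effect.

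The cost is SAP wording and one extra table from data already collected. The set becomes somewhat smaller, by an amount the documents do not allow one to state, and the documentation rule is itself a further post-baseline restriction. The added table does not address endpoints 8 to 11; for those, the revised description in item 2 is the safeguard. ITT stays the primary analysis.
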